#### 9 ADVERSE EVENTS

[figure not shown]
#### 9.1 Adverse Event

For the purposes of this trial, an adverse event is defined as any untoward medical event occurring after the subject's signing of the informed consent until they are exited from the trial. An adverse event can therefore be any unfavorable and unintended sign, symptom, or disease occurring after the subject started the clinical trial, without any judgment about causality. Any pre-existing medical condition that worsens during the trial will also be considered a new adverse event. Documentation regarding the adverse event should be made as to the nature, date of onset, end date, severity, relationship to study procedure, expectedness, action(s) taken, seriousness, and outcome of any sign or symptom observed by the investigator or reported by the patient upon indirect questioning.

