# **SYNOPSIS**

Protocol Title:	The TRANQUILITY 2 Trial: A Multi-Center Randomized, Double-Masked, Parallel Design, Vehicle-Controlled Phase 3 Clinical Trial to Assess the Efficacy and Safety of 0.25% -Reproxalap Ophthalmic Solution Compared to Vehicle in Subjects with Dry Eye Disease	
Protocol Number:	ADX-102-DED-023	
Investigational Product:	0.25% Reproxalap Ophthalmic Solution (reproxalap)	
Study Phase:	3	
Primary Objective(s):	To evaluate the efficacy of reproxalap, as assessed by conjunctival redness, Schirmer's Test, and symptoms after dosing prior to and during exposure to the with dry eye disease	
Overall Study Design:		
Structure:	Multi-center, double-masked, randomized parallel design trial	
Duration:	An individual subject's participation is estimated to be approximately 16-32 days.	
Controls: Vehicle Ophthalmic Solution (vehicle)		
Dosage/Dose Regimen:	Test article (reproxalap or vehicle) will be dosed topically in both eyes.  Test article will be administered QID on Day 1 (Visit 2). On Day 2 (Visit 3), test article will be administered once within 10 minutes prior to the CAE entry, once 45 minutes after initiation of the CAE, and once at CAE exit.	
Summary of Visit Schedule:	Three visits over the course of approximately 2 weeks:  • Visit 1 = Day -14 -16/+2, Screening	

Confidential Page 3 of 60

 
Visit 2 = Day 1, Randomization/Baseline
 
Visit 3 = Day 2 CAE & Study Exit
 
Subjects will be randomized 1:1 to receive reproxalap or vehicle.
 
Measures Taken to Reduce Bias:
 
ADX-102-DED-023 is a randomized treatment assignment, double-masked trial.
 
			
Study Population Characteristics:			
Number of Subjects:	Approximately 350 subjects are expected to be enrolled in the trial.		
Condition/Disease:	Dry Eye Disease (DED)		
Inclusion Criteria:	
 
Subjects must meet all of the following criteria:
 
1. 18 years of age (either gender and any race);
 
2. Ability to provide written informed consent and sign the Health Information Portability and Accountability Act (HIPAA) form;
 
3. Reported history of dry eye for at least 6 months prior to Visit 1;
 
4. Reported history of use or desire to use eye drops for dry eye symptoms within 6 months of Visit 1;
 
		
Exclusion Criteria:	Subjects must not meet any of the following criteria:		

Confidential Page 4 of 60

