# Visit 3 (Day 2, CAE■)

- Medical/Medication Update
- Adverse Event Query
- Urine Pregnancy Test (as needed)
- Visual Acuity (ETDRS)
- Slit Lamp Biomicroscopy
- Conjunctival Redness Photography
- Symptom Questionnaires:

- Pre-Dose #1 Tear Collection (30 +/- 5 minutes pre-dose)
- In-Office Dose #1 within 10 minutes prior to CAE Entry
- CAE Exposure (90 minutes) with:

Confidential Page 27 of 60

- In-Office Dose #2 (45 +/- 2 minutes into CAE exposure, administer by site staff)
- Post-CAE exit Tear Collection (started within 5 + 2 minutes)
- In-Office Dose #3 (started within 2 minutes post-tear collection)
- Symptom Questionnaires started within 10 minutes + 2 minutes post-Dose #3:

- Post-Dose #3 Tear Collection (started within 15 + 2 minutes of dose)
- Slit Lamp Biomicroscopy
- Intraocular Pressure
- Dilated Exam
- Study Exit

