#### 9.3.2 Reporting a Serious Adverse Event

To ensure subject safety, all serious adverse events, regardless of relationship to the investigational product, must be immediately reported. All information relevant to the serious adverse event must be recorded on the appropriate source documents. The investigator is obligated to pursue and obtain information requested by in addition to that information reported on the source document. All subjects experiencing a serious adverse event must be followed up and the outcome reported.

In the event of a serious adverse event, the investigator must notify immediately; obtain and maintain in his/her files all pertinent medical records, information, and medical judgments from colleagues who assisted in the treatment and follow-up of the subject; provide with a complete case history and inform the IRB of the adverse event within their guidelines for reporting serious adverse events.

Contact information for reporting serious adverse events (SAEs):

Confidential Page 33 of 60

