# 9.5 Procedures for Reporting Adverse Events

Adverse events that are ongoing at the end of the study visit will be followed. Phone calls will be placed with any subject who experiences an adverse event until the issue is resolved or the condition is considered ongoing and stable.

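### The adverse event definition stops at Study Exit on the day of the last dose, so the visible protocol sets no duty to report or count even a serious event that starts after exit

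*Combined protocol and SAP*

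**What the plan says.** Section 9.1 defines an adverse event, for this trial, as an untoward event that occurs from the subject's "signing of the informed consent until they are exited from the trial".

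The Synopsis gives four doses on Day 1 and three on Day 2, the later two being "once 45 minutes after initiation of the CAE, and once at CAE exit". Section 8.3.1 lists Visit 3 in this order: adverse event query, Dose #1, 90-minute CAE with Dose #2 part-way through, post-CAE tear collection, "In-Office Dose #3 (started within 2 minutes post-tear collection)", symptom questionnaires, "Post-Dose #3 Tear Collection (started within 15 + 2 minutes of dose)", slit lamp, IOP, dilated exam, Study Exit. No waiting period is given after the last dose or the dilation.

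Section 9.2 defines a serious adverse event as an adverse event with one of the listed outcomes. Section 9.3.2 says "all serious adverse events, regardless of relationship to the investigational product, must be immediately reported". Section 9.5 says "Adverse events that are ongoing at the end of the study visit will be followed", with telephone calls to subjects who have an adverse event. Section 10.4.9 calls an adverse event treatment-emergent if it begins or worsens once randomized dosing has started.

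**The concern.** The end of the window is tied to an administrative step, not to exposure. At Visit 3 that step comes shortly after the final dose and directly after a dilated exam. Suppose a subject leaves the site and telephones that evening with a new serious ocular problem. On the words of 9.1, that problem is not an adverse event.

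At stake is the reporting of uncommon but important events, and what the TEAE tables of a Phase 3 trial can claim. Efficacy conclusions are not affected.

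The schedule is also uneven. The screening CAE and dilated exam at Visit 1, before any study drug, are followed by an adverse event query at Visit 2. Day 1 doses are followed by the query at Visit 3. The on-treatment CAE, the last dose and the second dilated exam have no later query.

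**Working it through.** The plan states no figure to reproduce. The check is a reading of linked definitions, followed by simple timing.

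**Step 1: where the window ends.** The first sentence of 9.1 ends it at exit. The second sentence describes events "occurring after the subject started the clinical trial, without any judgment about causality" and names no end, but it is introduced as a consequence of the first, so it does not extend the window. If it were read as open-ended, the two sentences would conflict and would need reconciling.

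**Step 2: what depends on that definition.**
- 9.2: a serious adverse event must first be an adverse event, so it inherits the end at exit.
- 9.3.2: the duty covers all serious adverse events and gives no period of its own.
- 9.5: follow-up attaches to events already present when the visit ends. An event that starts later triggers no call.
- 10.4.9: the treatment-emergent rule has a start and no end, but it classifies only things that are already adverse events.

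**Step 3: does anything visible extend the window?**
- 8.3.1, Early Termination: monitoring runs through the trial, with nothing after exit.
- 8.4.2: unscheduled visits may include an adverse event assessment, but no period after exit is mentioned.
- 9.3: refers to IRB and regulatory requirements, but for adverse events as defined.
- Section 11: a general commitment to GCP and applicable requirements, with no window.

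Result: the defined window after Study Exit is 0 hours, for serious and non-serious events alike.

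**Step 4: time between each Day 2 dose and exit.** Inputs from 8.3.1, using nominal or latest permitted starts:
- CAE: 90 minutes, with Dose #2 at 45 minutes.
- Post-CAE tear collection: starts by 5 + 2 = 7 minutes.
- Dose #3: within 2 minutes of that collection.
- Final tear collection: starts by 15 + 2 = 17 minutes after Dose #3.

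Slit lamp, IOP and dilated exam have no stated duration; I assume 30 to 60 minutes in total. Tear collection times are not stated and are left out.
- Dose #3: 17 + (30 to 60) = 47 to 77 minutes, about 0.8 to 1.3 hours.
- Dose #2: (90 − 45) + 7 + 2 + (47 to 77) = 101 to 131 minutes, about 1.7 to 2.2 hours.
- Dose #1, given at CAE entry: 90 + 7 + 2 + (47 to 77) = 146 to 176 minutes, about 2.4 to 2.9 hours. Dosing at the earliest permitted time adds up to 10 minutes.

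Day 1 doses have until the Visit 3 query, roughly a day. Clock times are not stated.

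**The case against.** The strongest reply is that this is a coherent design choice. Sections 9.1 and 9.5 are compatible, the product is dosed only at the site, and delayed reactions to four doses are observed the next day in the same subjects by query, visual acuity and slit lamp. That is fair. What goes unobserved is the added late effect of the last doses, the on-treatment CAE and the dilation, not the late effects of the product as a whole.

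A reader might infer several stronger things that the documents do not support:
- *That all three Day 2 doses, 3 of 7, have almost no follow-up.* Step 4 shows otherwise for Doses #1 and #2. Only Dose #3, 1 of 7, is left with just the exit procedures.
- *That a calculable share of late reactions is lost.* The documents give no onset times, so any percentage would come from the assumed onset distribution.
- *That a serious event after exit could not be reported at all.* GCP and regulatory duties bind the trial, and 8.4.2 lets a site see a subject for safety. The supportable claim is only that the visible protocol sets no such duty.
- *That events between Dose #3 and exit are missed.* The only query listed at Visit 3 comes before dosing, but 8.3.1 requires monitoring of elicited and observed events throughout, so these events are covered.

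Unseen text also matters. A figure in Section 9, parts of the SAE reporting block, Appendices 1 and 2 and the SAP are not visible. The SAP governs statistical language and could settle how TEAEs are counted. The governing sentences of 9.1, 9.2 and 9.5 do, however, read as complete.

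**Conclusion.** The point holds as a gap in the visible protocol. An event that starts after Study Exit, serious or not, falls outside 9.1 and so outside the duties and tables built on it. The gap applies to every subject who exits at Visit 3. Its length is certain on the text: zero hours after exit. Its consequence in missed events is unknown.

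The conclusion rests on reading the second sentence of 9.1 as dependent on the first, and on no unseen text supplying a longer window. The 30 to 60 minutes assumed for the untimed exams affects only the illustration in Step 4. The matter is a worthwhile wording amendment for safety reporting, not a threat to the trial's efficacy inference.

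**What to change.** - **9.1:** end the window at a fixed, stated interval after the last dose instead of at exit, for any event the site becomes aware of. One benchmark within the protocol is at least the roughly one day that Day 1 doses receive.
- **9.3.2:** state that serious events learned of in that interval are reported, including after exit.
- **9.5:** state that such events are followed by telephone, as ongoing events already are.
- **10.4.9 and the SAP:** state that they count as TEAEs.

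Section 9.2 then inherits the new window unchanged. If text that is not visible already sets a period after exit, 9.1 only needs to be aligned with it.

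The cost is a wording amendment, a few more events (mostly volunteered) and slightly later closure of each subject's record. No extra visit or examination is needed. Because no active contact is added, late non-serious events would still be incompletely captured, and the study report should say so.

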#### 9.1.1 Severity

Severity of an adverse event is defined as a qualitative assessment of the degree of intensity of an adverse event as determined by the investigator or reported to him/her by the patient/subject. The assessment of severity is made irrespective of relationship to study procedures or seriousness of the event and should be evaluated according to the following scale:

Confidential Page 30 of 60

#### 9.1.2 Relationship to Study Procedures

The relationship of each AE to the study procedures should be determined by the investigator using these explanations. Decisive factors for the assessment of causal relationship of an AE to the study procedures include, but may not be limited to, temporal relationship between the AE and the procedure, known side effects of the procedure medical history, and/or concomitant medication:

- *Definite:* When there are good reason and sufficient documentation to demonstrate a direct causal relationship between study procedure and AE;
- *Probable:* When there are good reasons and sufficient documentation to assume a causal relationship in the sense of plausible, conceivable, likely but not necessarily highly probable.
- *Possible:* When there is sufficient information to accept the possibility of a causal relationship in the sense of not impossible and not unlikely, although the connection is uncertain or doubtful, for example; due to missing data or insufficient evidence.
- *None:* When there is sufficient information to accept a lack of a causal relationship, in the sense of impossible and improbable.
- *Unclassified:* When the causal relationship is not assessable for whatever reason due to insufficient evidence, conflicting data or poor documentation.

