#### 9.1.3 Expectedness

The expectedness of an adverse event should be determined based upon existing safety information about the study procedures. Therefore, the following definition will be used:

Confidential Page 31 of 60

- *Unexpected*: An adverse event that is not listed in the safety information available for the study procedure at the specificity or severity that has been observed.
- *Expected*: An adverse event that is listed in the safety information available for the study procedure at the specificity and severity that has been observed.
- *Not Applicable*: Any adverse event that is unrelated to the study procedure.

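### Sections 9.1, 9.1.2 and 9.1.3 grade AE causality and expectedness only against undefined 'study procedures'; no legible rule asks for a separate grade for the study drug

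*Combined protocol and SAP*

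**What the plan says.** - **Section 4** gives the trial's purpose as evaluating the efficacy and safety of reproxalap against vehicle.
- **Section 9.1** collects AEs from the subject's "signing of the informed consent until they are exited from the trial". The items to document include "severity, relationship to study procedure, expectedness, action(s) taken, seriousness, and outcome". The only causality item concerns the procedure.
- **Section 9.1.1** uses the same object: "The assessment of severity is made irrespective of relationship to study procedures or seriousness of the event".
- **Section 9.1.2** gives the rule: "The relationship of each AE to the study procedures should be determined by the investigator using these explanations". Its decisive factors include "temporal relationship between the AE and the procedure, known side effects of the procedure medical history, and/or concomitant medication", and the list is stated to be non-exhaustive. The grade *None* applies "When there is sufficient information to accept a lack of a causal relationship, in the sense of impossible and improbable".
- **Section 9.1.3** says: "The expectedness of an adverse event should be determined based upon existing safety information about the study procedures". Its *Not Applicable* category covers "Any adverse event that is unrelated to the study procedure", with no exception for an event related to the drug.
- **Section 9.3** requires all AEs to be reported. **Section 9.3.1** covers events graded definite, probable or possible that are also unexpected. **Section 9.3.2** requires immediate reporting of every SAE whatever its relationship to the investigational product.
- **Section 10.4.9** tabulates TEAEs by treatment group. Some of its breakdowns use the strongest relationship, without saying relationship to what.

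**The concern.** In a trial meant to assess a drug's safety, one expects the investigator to judge whether each event was related to the drug and whether it was expected for the drug. The written rules ask for both judgements against something else. The wording is consistent across four consecutive sections, so it does not look like a single slip.

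Two later parts of the plan depend on these grades: the 9.3.1 class of related and unexpected events, and the relationship tables in 10.4.9. If sites differ on whether instilling the drop is a study procedure, the same event can be graded on different bases. On neither basis does the recorded grade say what the investigator thought of the drug.

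**Working it through.** No figure in the plan needs reproducing. The check compares the rules, follows the two readings through, and counts how closely doses and procedures overlap.

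**1. What each rule names.** Sections 9.1, 9.1.1, 9.1.2 and 9.1.3 all name the study procedure(s). Section 9.3.2 is the only legible AE rule that mentions relationship to the investigational product, and it does so only to say that this relationship does not affect SAE reporting. It does not ask anyone to grade it. No legible passage defines the term. Section 8.3.1 lists the in-office doses under its heading on procedures to be performed at the visit, which favours including them but is not a definition.

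**2. The two readings, for a non-serious reaction to the drop.**

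- *Dosing is not a study procedure.* The investigator may grade *None*. Expectedness is then *Not Applicable*, and the event falls outside 9.3.1. Or the investigator may grade *Possible* because a procedure was close in time. The event then counts as related, but to the procedure, and its expectedness is judged against procedure safety information. In both cases the grade is not about the drug.
- *Dosing is a study procedure.* The drug is graded, but pooled with CAE exposure, tear collection, Schirmer's tests and examinations. A grade of *Probable* does not say which was meant.

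**3. Whether timing could separate drug from procedure.** Counts come from the visible Visit 2 and Visit 3 lists in 8.3.1. Doses: 4 + 3 = 7. Other eye procedures or examinations after Day 1 Dose #1:

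- tear collections 3 + 3 = 6
- Schirmer's tests 2
- CAE exposure 1
- slit-lamp examinations 2
- redness photography 2
- visual acuity 1, IOP 1, dilated exam 1

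Total: 6 + 2 + 1 + 2 + 2 + 1 + 1 + 1 = 16. This is a minimum, because the in-CAE assessments are redacted from the visit list. It excludes questionnaires and the pregnancy test.

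Largest gap from each dose to a nearby listed procedure:

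- Day 1 Dose #1: tear collection, up to 10 + 2 = 12 min
- Day 1 Dose #2: tear collection, up to 12 min
- Day 1 Dose #3: photography at 10 ± 2, so 8 to 12 min
- Day 1 Dose #4: Schirmer's test, up to 5 + 2 = 7 min
- Day 2 Dose #1: up to 10 min before CAE entry
- Day 2 Dose #2: inside the CAE, at 45 ± 2 min
- Day 2 Dose #3: within 2 min after tear collection

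So 7 of 7 doses are within 12 minutes of a listed procedure or inside the CAE. Counting only tear collection, Schirmer's tests and the CAE (6 + 2 + 1 = 9 procedures), it is 6 of 7. The exception is Day 1 Dose #3: taking the 30-minute wait as exact, the pre-Dose #4 Schirmer's test follows at (30 − 10) ± 2 = 18 to 22 minutes.

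**4. Tables affected.** Section 10.4.9 lists five TEAE breakdowns: SOC; SOC and PT; SOC, PT and severity; SOC, PT and relationship; SOC, PT, severity and relationship. Two of the five use relationship.

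**The case against.** The strongest reply is that dosing is a study procedure. Section 8.3.1 lists the doses among the visit procedures, and 9.3.2 treats relationship to the product as a known attribute of an event. On that view drug-caused events are graded. This has force, and it is why the point is limited to the absence of a *separate* drug grade. It remains an inference, and the pooled grade still does not identify the drug.

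A reader might infer that a drop reaction would necessarily be graded *None* and so miss 9.3.1. The documents do not support that. *None* has a demanding definition, the list of factors is open-ended, and the closeness of doses to procedures makes *Possible* a likely grade too.

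A reader might also infer that reports would be lost or the safety comparison compromised. Neither follows. Section 9.3 covers all AEs, 9.3.2 covers all SAEs, and the legible text gives 9.3.1 no timeline of its own. The 10.4.9 frequencies are by randomized, vehicle-controlled arm, and the visit procedures are not stated to differ between arms. Even a relationship table by arm still contrasts reproxalap with vehicle; it just does not say what the events were related to.

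Parts of Section 9 are redacted, and the eCRF and SAP were not seen. Either could hold a drug-relatedness field or define strongest relationship, so this caveat stands. Against it, the table of contents lists only severity, relationship to study procedures and expectedness under 9.1, and the legible definitions in 9.1.2 and 9.1.3 read as complete.

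Finally, one sentence saying what study procedures covers would settle which reading applies. It would not produce a drug-specific grade.

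**Conclusion.** The point holds for the legible protocol and should be fixed. Followed exactly, 9.1, 9.1.2 and 9.1.3 yield no separate grade of relatedness to, or expectedness for, the study drug. The effect is confined to those two grades, the 9.3.1 classification, and the meaning of strongest relationship in two of the five 10.4.9 breakdowns. The by-arm TEAE comparison, reporting of all AEs and immediate SAE reporting are intact.

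The overlap counts show why attribution cannot safely be rebuilt from timing afterwards. They do not measure harm, and the documents give no basis for estimating how many events would be misgraded. Confidence is high on the wording. It is lower on the practical effect, which depends on the unseen eCRF and SAP.

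**What to change.** - In 9.1, 9.1.2 and 9.1.3, record relationship to study drug separately from relationship to study procedures, and define study procedures as excluding dosing.
- Base drug expectedness on the drug's reference safety information.
- State that 9.3.1 applies to an unexpected AE related to the drug *or* to a study procedure. The procedure rating has to stay in that trigger because AEs are collected from consent, and Visit 1 includes a 90-minute CAE, a Schirmer's test, fluorescein staining and a dilated exam before any dose.
- State that the 10.4.9 relationship tables use the drug rating, with the procedure rating tabulated separately.

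The cost is protocol wording, one extra relationship field per AE, a second expectedness field if drug and procedure expectedness are held apart, and one extra table. The fields cost nothing if the eCRF already has them. No patients or visits are added. The split will be imperfect: with doses and procedures minutes apart, some AEs will be rated *Possible* for both.
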